AF ablation is now recognized as a second line therapy³, sometimes used as primary therapy prior to failure of an antiarrhythmic drug (AAD)⁴. The most common approach to AF ablation is based on Pulmonary Vein Isolation (PVI), but multiple alternate approaches are being used and studied (i.e. lines, complex fractionated electrograms (CFE), rotors, epicardial approach).

Radiofrequency (RF) energy is still predominantly used, with 3D mapping for both anatomical navigation and electrical mapping.

St. Jude Medical (SJM) provides a wide range of devices that can be used during atrial fibrillation (AF) ablation procedures and has recently introduced new devices such as the FlexAbility Ablation catheter with enhanced maneuverability and innovative irrigation and TactiCath Ablation Catheter with contact force sensing⁵.

Multiple papers address the treatment of AF from a clinical perspective⁶⁻⁹. This registry aims at collecting a large sample of real world cases focusing on the synergy between various tools and investigating their impact on procedural and clinical effectiveness. The outcomes will support recommendations for optimal techniques, evaluate overall procedural costs, provide feedback to designers for improved tools, create supporting data for randomized controlled trials designs and provide information on operator's choices from a vast variety of sites.

2 Registry Design

2.1 Purpose

The purpose of this registry is to assess the performance and clinical effectiveness of a combination of SJM mapping and ablation products in the treatment of subjects with atrial fibrillation (AF).

2.2 Objectives

- To confirm patient safety as part of the post market surveillance study.
- To assess performance of a combination of SJM products during procedures
- To assess the learning curve with a combination of SJM products.
- To collect operator feedback on a combination of SJM products
- To compare the acute and long-term effectiveness according to technique used.
- To analyze procedure efficiency according to technique used.

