2.3 Investigation Type

Post-market, international, multi-center, prospective, single arm observational registry.

SJM-CIP-10032 Ver. B

ABLATOR Study

October 20, 2015

This observational registry will be conducted in approximately 100 centers worldwide.

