2.5 Devices Used

In order to ensure a minimum level of uniformity across site practices and to enable comparison of acute and long-term effectiveness as well as procedure efficiency according to technique used, a combination of 2 types of devices from the pre-specified list must be used to be eligible in this registry.

List of devices to be used in this registry:

Combination of a minimum of 2 devices amongst:

Europe, Middle East Canada, Australia and New Zealand

- Ablation catheter: TactiCath or FlexAbility
 - Access with steerable sheath: Agilis NxT
 - Versatile diagnostic catheters: Inquiry Afocus II DL, Optima or Reflexion Spiral
- In case of advanced mapping, EnSite Velocity must be used.

US

- Ablation catheter: TactiCath
 - Access with steerable sheath: Agilis NxT
 - Versatile diagnostic catheters: Inquiry Afocus II DL, Optima or Reflexion Spiral
- In case of advanced mapping, EnSite Velocity must be used.

Asia

[figure not shown]
- Ablation catheter: Family of Therapy CoolFlex catheters
 - Access with steerable sheath: Agilis NxT
 - Versatile diagnostic catheters: Inquiry Afocus II DL, Optima or Reflexion Spiral
- In case of advanced mapping, EnSite Velocity must be used.

Only SJM commercially available shelf-stock will be used for the Registry. The manuals shipped with the SJM devices should be consulted. Successor models of the current approved devices can be used as well once they become available and market approved.

3 Data collection

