3.1 Registry Flow Chart

Figure 2: Flow Chart

All procedures will follow site standard of care at the site.

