One original signed consent document must be retained on file by the investigator and a second original signed consent document is provided to the subject (investigator's responsibility). The patient's legal rights will not be waived nor the appearance that these will be waived. Native non-technical language, understandable for the patient, will be used. Important new information that becomes available throughout the Registry will have to be provided in writing to new and existing patients. If relevant, all affected patients shall be asked to confirm their continuing informed consent in writing.

Baseline Visit

The following baseline information will be collected;

- Patient demographics
- Atrial fibrillation History (such as type, frequency, duration of atrial fibrillation and other arrhythmias other than AF),
- Cardiovascular history (NYHA class, LA diameter, LV EF% and degree of valvular heart disease),
- Cardiac medical history (pre-existing cardiac conditions and cardiac procedures).

Ablation procedure

- Devices used
- Ablation parameters
- Ablation success definition and result
- Operator feedback (Device combination chosen, device maneuverability, ease of use in combination with other device)
- Number, experience and type of attending personnel
- Definition of standard of care (follow-up procedures and occurrence)

6 and 12 Month Follow-up (+/- 30 days)

- Recurrence of atrial arrhythmias: list of atrial arrhythmias since last visit, classify episodes, duration of the episodes, (only events with source data evidence are to be recorded).
- Changes in therapy (new antiarrhythmic drug, redo procedures).
- In case of Repeat Ablation Procedures, reconnections and new ablations will be recorded.

Cardiovascular Serious Adverse Event

An adverse event is reportable in this registry when the event is deemed of cardiovascular origin and has the potential of leading to:

- Death
- A serious deterioration in the health of the subject, that can either result in:
 - o A life-threatening illness or injury OR
 - o A permanent impairment to a body structure or a body function OR
 - o An in-patient or prolonged hospitalization OR
 - o A medical or surgical intervention to prevent life-threatening illness or injury or permanent impairment to a body structure or a body function OR
 - o A malignant tumor
- Fetal distress, fetal death or a congenital abnormality or birth defect

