4.5 Statement of Compliance

The registry will be performed in accordance with the most current versions of the World Medical Association (WMA) Declaration of Helsinki, ISO 14155 and any regional and/or national regulations and will be compliant to this International Standard and any regional and national regulations, as appropriate.

The investigator shall not start enrolling patients or requesting informed consent from any patient prior to obtaining Ethics Committee approval and Competent Authority approval, if applicable, and authorization from the sponsor in writing.

In case additional requirements will be imposed by the Ethics Committee or Competent Authority they shall be followed, if appropriate.

5 Risks and Benefits of the clinical investigation

This registry will follow site standard practice procedures, therefore there are no risks or benefits associated with participating in this registry for the patient. A long term benefit for therapy delivery is expected based on the scientific outcome of the registry data analysis.

6 Statistical considerations

This is a post-market, international, multi-center, single arm observational registry. The objectives of this Registry are as follows:

- To confirm patient safety as part of the post market surveillance study.
- To assess performance of a combination of SJM products during procedures
- To assess the learning curve with a combination of SJM products.
- To collect operator feedback on a combination of SJM products
- To compare the acute and long-term effectiveness according to technique used.
- To analyze procedure efficiency according to technique used.

Up to 2,000 patients will be enrolled in this registry, which is expected to be adequate to address the objectives of this registry. Descriptive statistics will be used to summarize baseline and demographic data, procedural information, adverse events and recurrence of atrial arrhythmias. Continuous variables may be summarized using either mean, standard deviation and range, or median and interquartile range as applicable. Categorical variables will be summarized as frequencies and proportions. Kaplan-Meier time to event analysis may be used to summarize recurrent atrial arrhythmias. To assess learning curve, appropriate statistical analysis will be used to assess the influence of physician experience on procedural outcomes or adverse events.

7 Data Management

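### Techniques are compared only as performed; recording the planned technique before ablation would guard against sorting by acute response, a possible bias of unknown size

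*Combined protocol and SAP*

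**What the plan says.** Two objectives in section 2.2, both repeated in section 6, group patients by technique as performed: "To compare the acute and long-term effectiveness according to technique used" and "To analyze procedure efficiency according to technique used". Section 2.5 gives this comparison as one reason for its device rule, under which "a combination of 2 types of devices from the pre-specified list must be used to be eligible in this registry".

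No section defines a technique group. The background text before section 2 names pulmonary vein isolation (PVI) as the most common approach and adds that "multiple alternate approaches are being used and studied (i.e. lines, complex fractionated electrograms (CFE), rotors, epicardial approach" are further options. Section 2.5 instead connects technique with the combination of devices.

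There is no allocation. Section 2.3 describes a "Post-market, international, multi-center, prospective, single arm observational registry", and section 3.1 states "All procedures will follow site standard of care at the site".

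The Ablation procedure list in section 3.2 covers devices used, ablation parameters, the definition and result of ablation success, and "Operator feedback (Device combination chosen, device maneuverability, ease of use in combination with other device", among other items. It does not list a technique planned beforehand, a change of plan during the case, or a reason for one.

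Section 6 plans descriptive summaries and an optional Kaplan-Meier analysis of recurrence. It gives no method for comparing techniques, no adjustment for confounders, and no rule for a case whose technique changes part-way.

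**The concern.** A procedure may start with one approach and finish with another. If the reason for adding lesions or a catheter is that the first approach is not working, cases are sorted into groups by their acute response. Acute success is one of the outcomes compared, and acute response may also be related to recurrence and procedure time. Difficult cases would leave the simpler group and join the more extensive one, even if the two techniques were equally good.

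This differs from ordinary confounding by patient, site or operator. The sorting happens after treatment has started, so adjustment for baseline variables removes only the part of case difficulty that those variables predict. It also cannot be repaired at analysis, because intent that was not recorded before ablation cannot be reliably reconstructed.

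It matters because the background text says the results will feed advice on which techniques are best and will inform the design of randomized trials. A purely descriptive account of practice would not carry that weight.

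**Working it through.** **No plan figure to reproduce.** Section 6 says "Up to 2,000 patients will be enrolled in this registry, which is expected to be adequate to address the objectives of this registry". It gives no event rate, group split, effect size, error rate or power. Only N = 2,000 below comes from the documents. Every other input is an assumption made to show scale.

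**Set-up (no true technique effect).**
- Planned simpler technique 70% (S = 1,400); planned more extensive technique 30% (E = 600).
- Share of difficult cases in each planned group: d = 20%.
- 12-month recurrence: 25% in other cases, r = 45% in difficult cases, whatever technique is used.
- m = fraction of difficult planned-simple cases that receive additions and are then counted as extensive.

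**By planned technique.** Both groups: 0.80 × 0.25 + 0.20 × 0.45 = 29%. The gap is 0. It is exactly 0 only because equal case mix was assumed.

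**By technique used.** Cases changing group: M = S × d × m = 280m.
- Simple as used: (1,120 × 0.25 + (280 − M) × 0.45) / (1,400 − M)
- Extensive as used: (600 × 0.29 + M × 0.45) / (600 + M)

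| m | M | Simple as used | Extensive as used | Spurious gap | z |
|---|---|---|---|---|---|
| 10% | 28 | 393.4/1,372 = 28.7% | 186.6/628 = 29.7% | 1.0 points | 0.5 |
| 25% | 70 | 374.5/1,330 = 28.2% | 205.5/670 = 30.7% | 2.5 points | 1.2 |
| 50% | 140 | 343/1,260 = 27.2% | 237/740 = 32.0% | 4.8 points | 2.3 |
| 100% | 280 | 280/1,120 = 25.0% | 300/880 = 34.1% | 9.1 points | 4.4 |

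Here z is the gap divided by its unpooled standard error. For the last row, SE = √(0.25 × 0.75/1,120 + 0.341 × 0.659/880) = 0.0206. Section 6 specifies no such test, so z only shows the gap against sampling noise.

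**Range.** With d from 10% to 30% and r from 35% to 45%:
- m = 10%: 0.3 to 1.3 points
- m = 25%: 0.7 to 3.2 points
- m = 100%: 2.7 to 11.8 points

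The fraction m drives the result, and the documents say nothing about it.

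**Cross-check with other assumptions.** Take planned splits of 50:50 or 80:20, 10% to 30% difficult cases, 12-month success of 70% (easy) and 60% (difficult) or 75% and 50%, and m of 10% to 50%. The spurious deficit for the extensive group is then 0.2 to 9.7 points.

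**Procedure time.** Same cross-check grid, assuming 150 minutes for easy and 200 for difficult cases.
- Smallest gap (50:50, 10% difficult, m = 10%): (900 × 150 + 110 × 200)/1,010 − (900 × 150 + 90 × 200)/990 = 155.4 − 154.5 = 0.9 minutes.
- Largest gap (80:20, 30% difficult, m = 50%): (280 × 150 + 360 × 200)/640 − (1,120 × 150 + 240 × 200)/1,360 = 178.1 − 158.8 = 19.3 minutes.

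**Acute success.** The direction cannot be fixed. If difficult cases still fail after additions, the extensive group looks worse. If operators add lesions until the endpoint is met, the extensive group gains rescued successes, and the first approach's failures appear in neither group.

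**The case against.** The strongest reply is that the groups in the illustration are not the protocol's. It defines no simple and extensive groups, does not mention additions after a failed first approach, and links technique to device combination. That stands. The bias is a possibility that depends on how the groups are eventually drawn, and the missing definition is the prior gap.

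A reader might infer that the comparison will be biased, that the simpler technique will always look too good, and that the error is about 9 points. The documents do not support this. That figure requires every difficult planned-simple case to change group; at 25% changing it is 2.5 points. The direction for acute success is open.

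Nor would planned technique make the comparison fair. In a single-arm registry that follows site practice, the plan is itself chosen by site and operator, and section 6 plans no adjustment. This too stands.

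Describing techniques as used is legitimate in a registry of products in routine use, so replacing that summary outright would change the question. It should stay.

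Finally, section 3.2 summarises form content and is not the form itself, and it includes ablation parameters and the device combination chosen. A planned-technique field could exist on the form, though none is listed. The device-combination item is described as operator feedback from the procedure, not as a plan fixed before the first lesion.

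**Conclusion.** The point holds in a limited form. Both objectives group by something settled during the procedure, no planned technique or change is listed for collection, and section 6 has no analysis that deals with cases changing technique. The comparison can therefore be biased by sorting on acute response.

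Whether it will be, and by how much, cannot be known from the documents. Over the assumed inputs the spurious recurrence gap runs from under 1 point to about 12 points. The upper end needs all difficult cases to change group and 30% of cases to be difficult, with 45% recurrence among them.

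This is a cheap improvement. It does not show that the registry's results would be wrong. It is worth making before enrolment, since intent cannot be recovered afterwards.

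**What to change.** - **Section 3.2, Ablation procedure:** add two fields completed before the first lesion, for planned technique and planned device combination. Add a yes/no field for change during the procedure, with its reason.
- **Sections 2.2 and 6:** define the technique groups, saying whether they rest on lesion set, device combination or both, and how a case that changes is classified.
- **Section 6:** report acute success, recurrence and procedure time by planned technique alongside technique used. Base any recommendation between techniques on the planned-technique comparison, adjusted for baseline factors already collected, such as AF type, LA diameter and LVEF.

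The cost is a few form fields and some wording. The planned-technique comparison will include patients who received more than was planned, which may make true differences look smaller. Confounding by site and operator choice will remain and should be stated with the results.

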2.3 Investigation Type

Post-market, international, multi-center, prospective, single arm observational registry.

SJM-CIP-10032 Ver. B

ABLATOR Study

October 20, 2015

This observational registry will be conducted in approximately 100 centers worldwide.

2.4 Subject Population

All patients from participating sites who are indicated for an atrial fibrillation ablation procedure and willing to provide written Informed Consent may be enrolled in this registry.

Point of Enrollment

Patients are considered enrolled in this registry following provision of written Patient Informed Consent.

Expected duration of each subject's participation

The expected duration of each subject's participation is 1 year.

Expected duration of the registry

The expected duration of this registry is approximately 3 years: 2 years of enrollment and 1 additional year of follow up.

Number of Patients required to be included in the registry

Up to 2,000 patients will be enrolled in this registry.

2.5 Devices Used

In order to ensure a minimum level of uniformity across site practices and to enable comparison of acute and long-term effectiveness as well as procedure efficiency according to technique used, a combination of 2 types of devices from the pre-specified list must be used to be eligible in this registry.

List of devices to be used in this registry:

Combination of a minimum of 2 devices amongst:

Europe, Middle East Canada, Australia and New Zealand

- Ablation catheter: TactiCath or FlexAbility
 - Access with steerable sheath: Agilis NxT
 - Versatile diagnostic catheters: Inquiry Afocus II DL, Optima or Reflexion Spiral
- In case of advanced mapping, EnSite Velocity must be used.

US

- Ablation catheter: TactiCath
 - Access with steerable sheath: Agilis NxT
 - Versatile diagnostic catheters: Inquiry Afocus II DL, Optima or Reflexion Spiral
- In case of advanced mapping, EnSite Velocity must be used.

Asia

[figure not shown]
- Ablation catheter: Family of Therapy CoolFlex catheters
 - Access with steerable sheath: Agilis NxT
 - Versatile diagnostic catheters: Inquiry Afocus II DL, Optima or Reflexion Spiral
- In case of advanced mapping, EnSite Velocity must be used.

Only SJM commercially available shelf-stock will be used for the Registry. The manuals shipped with the SJM devices should be consulted. Successor models of the current approved devices can be used as well once they become available and market approved.

3 Data collection

3.1 Registry Flow Chart

Figure 2: Flow Chart

All procedures will follow site standard of care at the site.

3.2 Case Report Forms Content

Table 1: Data Collection

CRFs \ Visit	Enrollment & Baseline	Ablation Procedure	6 and 12 Months
Enrollment: Informed Consent Process	X		
Baseline: Demographics, Cardiovascular History, AF History, Medical History	X		
Ablation procedure		X	
Device user experience		X	
Follow Up Log*			X
Repeat procedure			(X)
Cardiovascular Serious Adverse Event	(X)	(X)	(X)
Withdrawal	(X)	(X)	(X)
Death	(X)	(X)	(X)

(X) if applicable

* Telephone or office visit

Enrollment & Informed Consent Process

The investigator is responsible for screening subjects for this registry and for obtaining patient informed consent, as applicable per local regulations. Provision of the Informed Consent is mandatory. Informed Consent is required from all patients (or their legal representatives) prior to participation in the investigation. The process of obtaining Informed consent shall comply with the most recent version of the declaration of Helsinki, ISO 14155 and all applicable regulations. The principal investigator or his/her authorized designee will conduct the Informed Consent Process. This process will include a verbal discussion with the patient on all aspects of the clinical investigation that are relevant to the patient's decision to participate in the clinical investigation. It is crucial that this discussion is documented in the source documents (read hospital records of the patient).

The patient will be provided with the informed consent form that is written in a language that is understandable to the patient and has been approved by Ethics Committee. The patient is given ample time to consider participation and ask questions if necessary.

In order to avoid any possible coercion or undue improper influence on, or inducement of the patient to participate, the Sponsor requests the investigator to only sign the informed consent form once the patient has signed and dated the document and therefore decided to participate in the investigation.

Informed Consent of a patient shall always be indicated by personally dated signature of the patient and by the investigator responsible for conducting the informed consent process. It is crucial that the signature of the informed consent is documented in the source documents (read hospital records of the patient).

One original signed consent document must be retained on file by the investigator and a second original signed consent document is provided to the subject (investigator's responsibility). The patient's legal rights will not be waived nor the appearance that these will be waived. Native non-technical language, understandable for the patient, will be used. Important new information that becomes available throughout the Registry will have to be provided in writing to new and existing patients. If relevant, all affected patients shall be asked to confirm their continuing informed consent in writing.

Baseline Visit

The following baseline information will be collected;

- Patient demographics
- Atrial fibrillation History (such as type, frequency, duration of atrial fibrillation and other arrhythmias other than AF),
- Cardiovascular history (NYHA class, LA diameter, LV EF% and degree of valvular heart disease),
- Cardiac medical history (pre-existing cardiac conditions and cardiac procedures).

Ablation procedure

- Devices used
- Ablation parameters
- Ablation success definition and result
- Operator feedback (Device combination chosen, device maneuverability, ease of use in combination with other device)
- Number, experience and type of attending personnel
- Definition of standard of care (follow-up procedures and occurrence)

6 and 12 Month Follow-up (+/- 30 days)

- Recurrence of atrial arrhythmias: list of atrial arrhythmias since last visit, classify episodes, duration of the episodes, (only events with source data evidence are to be recorded).
- Changes in therapy (new antiarrhythmic drug, redo procedures).
- In case of Repeat Ablation Procedures, reconnections and new ablations will be recorded.

Cardiovascular Serious Adverse Event

An adverse event is reportable in this registry when the event is deemed of cardiovascular origin and has the potential of leading to:

- Death
- A serious deterioration in the health of the subject, that can either result in:
 - o A life-threatening illness or injury OR
 - o A permanent impairment to a body structure or a body function OR
 - o An in-patient or prolonged hospitalization OR
 - o A medical or surgical intervention to prevent life-threatening illness or injury or permanent impairment to a body structure or a body function OR
 - o A malignant tumor
- Fetal distress, fetal death or a congenital abnormality or birth defect

A planned hospitalization for a pre-existing condition is not considered a serious adverse event.

Potential Cardiovascular Serious Adverse Events (SAEs) include but are not limited to the following:

Abnormal ECG, Angina (chest pain), Arrhythmia, AV fistula, Complete heart block, Coronary artery injury, Cardiac perforation, Cardiac Thromboembolism, CHF exacerbation – fluid overload, Component damage to ICD or implantable pacemaker, Death, Dislodgement of implantable cardioverter defibrillator or permanent pacing lead, Endocarditis, Exacerbation of pre-existing atrial fibrillation, Heart Failure, Hypotension, Inadvertent AV block (complete heart block), Left atrial/esophageal fistula, Myocardial infarction, Obstruction/perforation/damage of the vascular system, Palpitation, Pericardial effusion/cardiac tamponade, Pericardial effusion without tamponade, Pericarditis, Pulmonary vein dissection, Pulmonary vein stenosis, Pulmonary vein thrombus, Temporary or complete heart block, Unintended (in)complete AV, sinus node, heart block/damage, Vessel wall/valvular damage or insufficiency and Ventricular arrhythmia requiring defibrillation.

Procedure for assessing, recording and reporting SAEs:

Cardiovascular SAEs must be reported following local regulation, no later than 7 days from site being made aware of the event. All cardiovascular SAEs between patient enrollment and end of registry must be reported to the sponsor and to the local ethics committees, as per local regulations.

Should an SAE occur, complete and submit an Adverse Event form to St. Jude Medical.

Additional information can be requested, if necessary, by the Sponsor for reporting of SAEs to regulatory authorities. The investigator must notify the Ethics Committee, if appropriate, in accordance with national and local laws and regulations.

Death

All patient deaths that occur during this registry must be reported to SJM within 72 hours of the center becoming aware of the death. An Adverse Event form should be completed for all deaths at all sites.

Protocol Deviations

Investigators are required to adhere to the study protocol, signed Investigator's Agreement, applicable federal (national) or state/local, laws and regulations, and any conditions required by the Ethics Committee or applicable regulatory authorities. A protocol deviation is used to describe situations in which the study protocol was not followed. All deviations from the study protocol must be reported to SJM.

Withdrawals

All reasonable efforts should be made to retain the patient in the Registry. If a patient concludes their participation in the registry, the patient's future management will not be changed by this decision, whether it is voluntary or otherwise. Should a patient withdraw and conclude participation in the registry, document the information in the withdrawal form (CRF) as soon as possible.

4 Registry Conduct

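### Does the lack of a common definition of acute ablation success spoil the acute comparison by technique?

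*Combined protocol and SAP*

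**What the plan says.** Among the objectives in Section 2.2, repeated in Section 6, is "To compare the acute and long-term effectiveness according to technique used". The introductory text before Section 2 adds an ambition: "The outcomes will support recommendations for optimal techniques". It also describes a varied field: "The most common approach to AF ablation is based on Pulmonary Vein Isolation (PVI), but multiple alternate approaches are being used and studied".

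For the acute outcome, the ablation procedure list in Section 3.2 names "Ablation success definition and result", next to items such as "Ablation parameters". No common definition of acute success appears anywhere. Section 3.1 leaves procedures to each site's usual care, and Section 2.3 expects about 100 centers. The one stated uniformity measure is the device-combination rule in Section 2.5, which opens "In order to ensure a minimum level of uniformity across site practices and to enable comparison of acute and long-term effectiveness".

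On analysis, Section 6 says: "Descriptive statistics will be used to summarize baseline and demographic data, procedural information, adverse events and recurrence of atrial arrhythmias". For the learning curve it says "appropriate statistical analysis will be used to assess the influence of physician experience on procedural outcomes or adverse events". It specifies no analysis by technique and does not mention the recorded success definitions.

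**The concern.** Section 2.5 shows that the sponsor thought about comparability for this very objective, but its rule fixes which devices are used and not how success is judged. One operator may count a procedure as successful on a looser criterion than another. If the looser criterion is more common with one technique, that technique's pooled success rate is higher even when the two perform identically. A reader could then take a difference in strictness for a difference in effectiveness, in a registry meant to inform recommendations on technique.

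What is at stake is the acute half of one of six objectives. A learning-curve analysis of acute success would be affected only if definitions also varied with operator experience.

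**Working it through.** **No figure of the plan to reproduce.** The only sample-size figure is the ceiling of 2,000 patients. The documents give no success rate, effect size, significance level or power. Every success rate below is therefore an assumption.

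**What has to be true for bias.** Three conditions are needed together:

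1. Definitions differ between procedures.
2. They differ in strictness.
3. Their mix differs between techniques.

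Section 3.2 makes the first possible. The documents show none of the three and exclude none. A fourth condition is that the analyst pools across definitions, and Section 6 contains no such instruction.

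**Size if all four hold.** Let two techniques perform identically. Success is 0.95 under a looser definition and *s* under a stricter one. Technique A uses the looser definition in a share *w* of cases, technique B in a share 1 − *w*.

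- Pooled rate A = *w* × 0.95 + (1 − *w*) × *s*
- Pooled rate B = (1 − *w*) × 0.95 + *w* × *s*
- Artefact = A − B = (2*w* − 1) × (0.95 − *s*)

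| Looser share, A vs B | *s* = 0.93 | *s* = 0.85 |
|---|---|---|
| 50/50 | 0 | 0 |
| 60/40 | 0.942 − 0.938 = 0.004 | 0.910 − 0.890 = 0.020 |
| 80/20 | 0.946 − 0.934 = 0.012 | 0.930 − 0.870 = 0.060 |

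Within one definition the artefact is 0.95 − 0.95 = 0, or *s* − *s* = 0, whatever the mix.

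**How uneven the mix could be by chance.** Assume two techniques, 50 equal sites each, one technique and one definition per site, half of sites looser, and no link between definition and technique.

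- SD of the difference in looser shares = √(2 × 0.25 / 50) = 0.100.
- SD of the artefact = 0.100 × (0.95 − *s*), which is 0.002 for *s* = 0.93 and 0.010 for *s* = 0.85, that is 0.2 to 1.0 points.
- By exact binomial calculation, a gap in shares of at least 0.20 has probability 0.057, and one of at least 0.60 has probability 1.1 × 10⁻⁹.

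The 50 sites are not anchored in the documents. With 25 sites per technique the SD of the difference in shares is √(0.5/25) = 0.141, and the artefact SD is 0.3 to 1.4 points. With 10 sites it is √(0.5/10) = 0.224, and 0.4 to 2.2 points. Use of several techniques within a site would lower these figures. The 80/20 row would need definitions to be linked to technique.

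**What a common endpoint would gain.** Suppose every procedure were also classified by whether all pulmonary veins were isolated at the end.

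- Approaches that do not aim at isolation would have no acute comparison on that endpoint.
- A repeat case whose veins were already isolated fits both an isolated and a not-attempted category.
- Unverified cases bring their own artefact. With true isolation of 0.95 in both groups and assumed unverified shares of 0.02 and 0.10, counting unverified as failure gives 0.98 × 0.95 − 0.90 × 0.95 = 0.931 − 0.855 = 0.076. Counting it as success gives (0.931 + 0.02) − (0.855 + 0.10) = 0.951 − 0.955 = −0.004.

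On these assumptions, 7.6 points is larger than the largest artefact in the table.

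**The case for a change.** The strongest case for a change is that recording a definition does not commit anyone to using it. Section 6 is silent, so groupings could be chosen after results are seen. The objective speaks of comparing, and plain proportions by technique mislead as readily as a formal test if the endpoints are unlike. If technique means lesion approach, definitions might well follow technique, because an approach aimed at isolating veins and one aimed at rotors need not share an acute endpoint. A sentence in Section 6 would cost little.

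The silence is real, and so is the possibility of a link. Neither makes the plan wrong as written. Section 6 sets out no comparison by technique, so it also sets out no pooled one; following it literally does not produce the misleading figure. An analyst who finds a definition field beside the result field has an obvious reason to cross-tabulate them before comparing anything. Where definitions and technique coincide entirely, that table shows at once that the acute comparison is not supported. A prior rule would reach the same end, because stratification then has no overlap to work with. Classifying definitions without knowledge of technique may not be feasible either, since the wording of a definition can reveal the approach.

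The unseen form also matters. The line in Section 3.2 summarises content; the field may be a fixed list, and isolation status may already sit among the ablation parameters.

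**Conclusion.** The observation is accurate, but it is missing detail that analysts can fill sensibly, not a fault that makes the plan give a wrong answer. Leaving success to local judgement and recording the criterion suits a registry that follows usual care and sets out to learn what operators choose across many sites. Section 3.2 treats follow-up practice in the same way, by recording it.

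The harm depends on definitions differing, differing in strictness, being unevenly spread, and then being pooled. On the assumed rates it is 0 within a definition. When definitions are unrelated to technique, the pooled artefact has an SD of 0.2 to 1.0 points under the 50-site assumption, or up to 2.2 points with 10 sites per technique. The 6-point figure requires a link to technique that the documents do not show. Even there, the remedies would mostly withhold the comparison. No false-positive rate is attached, because Section 6 specifies no test of acute success between techniques. No change to the plan follows.
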